**Table 3: Criteria for Potentially Clinically Significant Laboratory Tests**

Parameter	SI Unit	Lower Limit	Higher Limit
Biochemistry			
Albumin	g/L	<25 g/L	
Alanine Aminotransferase (ALT)	U/L		≥3*ULN
Alkaline Phosphatase (ALP)	U/L		≥3*ULN
Aspartate Aminotransferase (AST)	U/L		≥3*ULN
Bilirubin, Direct	umol/L		>1.5*ULN
Bilirubin, Total	umol/L		>1.5*ULN
Bicarbonate	mmol/L	<LLN	
Blood Urea nitrogen	mmol/L		>2.5*ULN
Chloride	mmol/L	<90 mmol/L	>115mmol/L
Creatinine	umol/L		≥178.8 umol/L
Creatine kinases	U/L		≥3*ULN
Glucose	mmol/L	<3.05 mmol/L	≥8.88 mmol/L
Potassium	mmol/L	<3.5 mmol/L	>5.5 mmol/L
Sodium	mmol/L	<130 mmol/L	>150 mmol/L
Hematology			
Hemoglobin	g/L	<0.9*LLN	
Hematocrit	%	<0.9*LLN	
Platelet Count	10  /L	<LLN	
Urinalysis			
Specific Gravity		<0.9*LLN	>1.1*ULN
pH		<LLN	
Protein			>2+
Glucose			>1+
Blood			>2+

LLN: Lower limit of normal value provided by the laboratory  
 ULN: Upper limit of normal value provided by the laboratory

Descriptive statistics will be used for continuous data and frequency counts and percentages for categorical data. A shift table from baseline, by treatment group and protocol specified time points, of normal, abnormal low, and abnormal high records will also be summarized for hematology and chemistry data with marginal totals using frequency counts and percentages.

All laboratory data will be listed for the safety set.

### 7.3. Vital Signs

Descriptive statistics for vital signs (e.g., systolic and diastolic blood pressure, respiratory rate, temperature, and pulse rate) and their changes from baseline at each post-baseline visit will be presented by treatment group and overall.

Vital sign values will be considered PCS if they meet both the observed value criteria and the change from baseline criteria listed in Table 4. The number and percentage of subjects with PCS baseline and/or post-baseline values will be tabulated by treatment group and overall.

The percentages will be calculated relative to the number of subjects with values for each vital sign parameter in each treatment group at the analysis visit. The numerator is the total number of subjects with at least 1 PCS vital sign value at the analysis visit. A supportive listing of subjects with post-baseline PCS values will be provided including the subject number, site, baseline, and post-baseline PCS values.

**Table 4: Criteria for Potentially Clinically Significant Vital Signs**

Vital Sign Parameter	Flag	Criteria a	
		Observed Value	Change from Baseline
Systolic blood pressure (mmHg)	High	≥180	Increase of ≥20
	Low	≤90	Decrease of ≥20
Diastolic blood pressure (mmHg)	High	≥105	Increase of ≥15
	Low	≤50	Decrease of ≥15
Pulse rate (beats per minute)	High	≥120	Increase of ≥15
	Low	≤50	Decrease of ≥15

a A post-baseline value is considered as a PCS value if its meets both criteria for observed value and change from baseline.

All vital signs data will be listed for the safety set.

### 7.4. Physical Examination Findings

Any relevant findings from the baseline physical examination are to be reported on the medical history. Any relevant findings from the post-baseline physical examination are to be reported as AE's. No separate physical examination findings were collected to summarize.

### 7.5. Complete Ophthalmic Exam

Results of the ocular assessments will be summarized by shift tables showing the shift from baseline in the individual slit-lamp examination and indirect ophthalmoscopy endpoint. These will be provided by treatment group, overall and visit for study eye and fellow eye. The visits to be presented are Month 12, Month 24, and LOV.

Any relevant findings from the post-baseline ophthalmic examination are to be reported as AEs.

The change from baseline in chronic (first measurement of the day) IOP will be summarized over time by treatment group. In addition, the incidence of IOP above specified thresholds (i.e., >21 mmHg at pre-injection/chronic (first measurement of the day); >30 mmHg post injection) will be summarized by treatment group and overall, protocol specified timepoint (at Month 12 and Month 24 readout, respectively) and over the whole study.

The mean change from baseline in the chronic IOP  $\pm$  the standard error will be plotted over time by treatment group.

Details of the ocular assessments will be provided in listings for the safety set and for IOP, the ITT set.

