4.2. Risk/Benefit

The Phase 1 (Study POT-CP043014; NCT02461771) and Phase 2 (Study POT-CP121614; NCT02503332) studies provide supporting evidence of a positive benefit-risk profile for the use of pegcetacoplan in treating patients with AMD, specifically patients with GA. These

preliminary results of an up to 28% reduction of GA progression rate support the evaluation of pegcetacoplan in a Phase 3 study.

The reported safety data from these studies demonstrated an acceptable safety and tolerability profile with no clinically significant safety concerns observed. A total of 178 patients have received at least 1 dose (15 mg/injection) of pegcetacoplan as part of these studies. In the Phase 2 study in patients with GA an imbalance in new exudation in subjects treated with pegcetacoplan was observed. Section 4.1.4 provides a summary of the study design and key results from both studies.

The safety monitoring practices employed by this protocol (complete ophthalmologic exam, IOP monitoring, OCT, fluorescein angiography, vital signs, hematology, serum chemistry, urinalysis, physical exam, vital signs, and AE questioning) are adequate to protect the subjects' safety. There are also risks associated with the ophthalmic procedures required for participants in this study. However, these are all standard procedures that are widely performed in ophthalmology.

In the days following any IVT injection, patients are at risk of developing sterile or infectious intraocular inflammation (eg, endophthalmitis). In recent studies conducted with pegcetacoplan IVT from a single manufacturer, events of transient moderate and severe intraocular inflammation have been observed. Other risks of IVT injection include traumatic cataract, retinal detachment, increased IOP, and hemorrhage.

The amount of blood (See Section 9.16) planned for collection from each subject over the 24 months of the study does not pose an undue risk in this patient population.

There is a potential health benefit for trial participants from receipt of study drug. If efficacious, pegcetacoplan is expected to alter the course of GA and slow its rate of progression.

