9.13. Complete Ophthalmic Exam

The complete ophthalmic exam will consist of the following:

- External examination of the eye and adnexa.
- Routine screening for eyelids/pupil responsiveness (including ptosis, abnormal pupil shape, unequal pupils, abnormal reaction to light, and afferent pupillary defect).
- Slitlamp examination (cornea, anterior chamber, iris, lens, aqueous reaction [cells and flare]). Please see Appendix H for grading scales.
- Dilated fundus exam including evaluation of retina and vitreous (ie, posterior segment abnormalities, retinal hemorrhage/detachment, and vitreal hemorrhage density and vitreous cells). Vitreal hemorrhage density and vitreous cells grading scales are outlined in Appendix I.
- IOP measurement—A measurement of intraocular pressure will be conducted using either Tono-Pen or Goldmann applanation tonometer as outlined in the MOP. This should be performed prior to dilating the eyes and the same method should be used for all measurements in the same subject throughout the study.

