12.8. Safety Analyses

Adverse events will be collected from the time of the first study drug administration until a subject completes the study or discontinues prematurely. Treatment-emergent adverse events are defined as those AEs that develop or worsen after the first dose of study medication and up to 30 days beyond the last dose of study medication. The current version of MedDRA will be used to classify all AEs. Treatment-emergent adverse events will be summarized by System Organ Class and Preferred Term, in accordance with the MedDRA coding dictionary. The number of subjects reporting each AE Preferred Term will be tabulated for all TEAEs and separately for those considered as related to study treatment by the investigator or designee. Number of

subjects reporting SAEs will also be tabulated. Adverse event summaries will be presented for each treatment group separately.

Adverse events will be summarized by MedDRA coding terms, and separate tabulations also will be produced for related AEs (those considered by the investigator as definitively drug related), SAEs, and discontinuations due to AEs. Vital signs data and findings from physical and ophthalmologic examinations will be tabulated for changes over time on study. Laboratory parameters will be summarized for changes across study by using descriptive statistics. Separate summaries will be prepared for systemic (nonocular) and ocular AEs, with events in the study eye and nonstudy eye summarized separately

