## 7. SAFETY ANALYSES

Safety analyses will be performed using the Safety set. Safety variables include adverse events (AEs), deaths, clinical laboratory results, vital signs, incidence of ADA against pegcetacoplan, ocular assessments (e.g., NL-BCVA, IOP and ophthalmic examinations), and ocular imaging.

At the time of the Month 12 reporting, safety summaries will be produced based on the complete Month 12 data. At the time of the final study reporting, safety summaries will be produced based on cumulative data.

For each safety variable, the last value collected before the first dose of investigational product will be used as baseline for all analyses of that safety variable. Last Observed Value (LOV) will be defined as the last valid assessment obtained after baseline. The LOV will be presented for the Month 12 reporting as well as the final study reporting.

All safety analyses will be conducted according to the actual treatment the subject received. Unless otherwise specified, all safety summaries will be performed on the Safety set.

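### SAP 7.5 shows graded eye-exam shifts only at Month 12, Month 24 and last observed value, so most transient intraocular inflammation will not be summarised by cell or flare grade by arm

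*SAP*

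**What the plan says.** SAP 7.5 plans "shift tables showing the shift from baseline in the individual slit-lamp examination and indirect ophthalmoscopy endpoint", by treatment group and overall, for the study eye and the fellow eye. It then limits the display: "The visits to be presented are Month 12, Month 24, and LOV". SAP 7 gives the meaning of the last item: "Last Observed Value (LOV) will be defined as the last valid assessment obtained after baseline". For a subject who completes, that normally repeats the final displayed visit. Under SAP 13.4.1 an unscheduled or early-termination exam stands in for a nominal visit only when that visit's own result is missing.

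The exam is graded. Protocol 9.13 lists "Slitlamp examination (cornea, anterior chamber, iris, lens, aqueous reaction [cells and flare]). Please see Appendix H for grading scales" and adds: "Vitreal hemorrhage density and vitreous cells grading scales are outlined in Appendix I". The scales printed in the two appendices cover flare, anterior chamber cells and vitreous cells. Appendices A to D schedule the slit-lamp exam and dilated ophthalmoscopy at every clinic visit.

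Protocol 4.2 places the risk of sterile or infectious inflammation in the days after an intravitreal injection. It reports that, in recent studies with pegcetacoplan from a single manufacturer, "events of transient moderate and severe intraocular inflammation have been observed".

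Inflammation is also reported by other routes. SAP 7.1 tabulates endophthalmitis and intraocular inflammation events by preferred term for each eye and, for the study eye, per injection. SAP 7.5 asks that relevant exam findings be recorded as adverse events, and it lists the ocular assessments. SAP 13.6 puts all assessments in the listings.

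**The concern.** A shift table at two fixed visits suits lasting change, such as cataract. It suits a short-lived event poorly. An eye with marked cells at Month 3 that is clear at Month 12 and Month 24 is counted as having no shift.

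The adverse-event tables cover the same risk, but they measure something different. They hold findings that the investigator judged relevant, on the mild, moderate or severe scale of Protocol 11.3.2, which turns on the need for intervention and on daily activities rather than on cell or flare grade. As planned, no table sets graded inflammation at any time against the events reported, arm by arm.

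The SAP gives this kind of any-time view elsewhere. In the same section, the incidence of raised intraocular pressure is summarised over the whole study. SAP 13.6 uses all post-baseline assessments to find potentially clinically significant values. SAP 7.7 compares reading-center findings of choroidal neovascularization (CNV) with reported events in detail.

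**Working it through.** The plan gives no figure to reproduce here. Two checks were made: a count of exams, and a timing check under stated assumptions.

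**1. Exams shown (full schedule, Appendices A to D)**

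- Monthly arms: 12 in year 1 + 12 in year 2 = 24 post-baseline exams. Shown: Month 12 and Month 24. 2/24 = 8.3%; not shown, 22.
- EOM arms: 12 + 6 = 18. Shown: 2. 2/18 = 11.1%; not shown, 16.

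The EOM count falls under the temporary COVID-19 schedule, which lets EOM subjects skip non-dosing visits.

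**2. Would a post-injection episode reach a scheduled exam at all?**

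Protocol 7.3.2 tells sites to take the order of procedures from the Visit Schedule, which lists the slit-lamp exam before the injection. The next scheduled exam therefore falls about 30 days after a dose, or about 60 days in the EOM arms in year 2.

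Assumptions, not in the documents: onset on day 1 to 7 after any one injection, all equally likely; duration D days; exams on target days. An episode starting on day o after an injection on day d is active from d + o to d + o + D. It is displayed if that interval contains day 360 or day 720. It is seen at some scheduled exam if the interval contains any exam day. There are 24 × 7 = 168 injection-onset pairs in the monthly arms and 12 × 7 = 84 in the EOM arms.

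| D (days) | Monthly: displayed | Monthly: any scheduled exam | EOM: displayed | EOM: any scheduled exam |
|---|---|---|---|---|
| 7 to 21 | 0% | 0% | 0% | 0% |
| 28 | 12/168 = 7.1% | 144/168 = 85.7% | 0% | 36/84 = 42.9% |
| 42 | 14/168 = 8.3% | 168/168 = 100% | 0% | 42/84 = 50.0% |
| 56 | 22/168 = 13.1% | 100% | 8/84 = 9.5% | 66/84 = 78.6% |
| 63 | 28/168 = 16.7% | 100% | 14/84 = 16.7% | 84/84 = 100% |

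This leads to two results. An episode of 21 days or less ends by day 7 + 21 = 28, before any scheduled exam, so showing every scheduled visit would not reveal it; only an unscheduled exam could. An episode of about 4 to 9 weeks is often or always seen at a scheduled exam, yet at most 16.7% of such episodes fall on a displayed one. A worst-grade table therefore needs the scheduled exams for the longer episodes and the unscheduled exams for the short ones.

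**The case against.** The strongest reply is that the risk already has its own analysis. Inflammation events are counted at any time, by preferred term, by eye and per injection; ocular events are also shown by maximum severity; endophthalmitis must be reported as a serious event (Protocol 7.5.3); and the staff who inject do not assess adverse events (SAP 3.3). All of that stands, and it limits the point to the graded summary by arm.

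The documents do not support four stronger readings that a reader might infer:

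- **That transient inflammation cannot appear in these tables.** It appears if still active at Month 12, at Month 24 or at an early leaver's last valid exam, or if an unscheduled exam fills a missing visit.
- **That under-recording of inflammation as adverse events could not be detected.** The listings hold every graded exam, so a subject-by-subject comparison is possible. What is missing is a summary of it.
- **That the undisplayed share of exams, 22/24 or 16/18, measures inflammation lost.** It counts exams, not episodes. Under the timing assumptions, short episodes fall between scheduled exams whichever visits are shown.
- **That the SAP contradicts Protocol 12.8.** The protocol says "findings from physical and ophthalmologic examinations will be tabulated for changes over time on study". That sets no visit frequency, and shifts to Month 12 and Month 24 are changes over time.

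**Conclusion.** The concern holds as a gap in descriptive safety reporting. Under the full schedule the shift tables show 2 of 24 or 2 of 18 scheduled exams plus the last observed value. Under the stated timing assumptions they capture no episode of 21 days or less, and at most 16.7% of episodes lasting up to 63 days. Those percentages depend on assumed onset, assumed duration and exact visit days; the visit windows and the COVID-19 schedule would shift them. They also leave out unscheduled exams and the last exam of early leavers, which would add some episodes.

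No efficacy test, error rate or adverse-event analysis is affected. What would be lost is a by-arm view of how severe graded inflammation became at any time, to set beside the reported events. The change should be made because it is cheap and the data are already collected.

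**What to change.** In SAP 7.5, keep the Month 12, Month 24 and last-observed-value tables. Add, by eye and treatment group, a shift from baseline to the worst post-baseline grade over scheduled, unscheduled and early-termination exams, for anterior chamber cells, flare and vitreous cells. Limit the addition to these three items, because a worst grade needs an ordered scale and these are the ones graded in Appendices H and I.

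Two cautions belong with the tables:

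- A maximum tends to rise with the number of exams, 24 against 18. Show the results by regimen as well, with the monthly and EOM sham arms (SM and SEOM) unpooled, so that each active arm is read against sham subjects on the same schedule. SAP 4 otherwise pools the sham arms.
- Unscheduled exams are driven by symptoms or events, and their frequency may differ between injected and sham eyes. Show the maximum over scheduled exams alone beside the main table. That version will miss the shortest episodes.

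The cost is a paragraph of SAP text and a few tables. No visit, procedure or data collection changes.

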## 7.6. NL-BCVA

The number and percentage of subjects who lost letters compared with baseline at each visit based on NL-BCVA in the study and fellow eye will be presented. The three categories are  $\geq 15$ ,  $\geq 15 - < 30$  and  $\geq 30$  ETDRS letters.

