This is a 24-month, Phase 3, multicenter, randomized, double-masked, sham-injection controlled study to assess the efficacy and safety of multiple IVT injections of pegcetacoplan in subjects with GA secondary to AMD.

The study will randomize approximately 600 subjects across approximately 100 multinational sites. Subjects will be screened within 28 days before receiving pegcetacoplan or sham injection. Upon entry into the study, subjects will be assigned a screening number. Subjects who meet all inclusion and none of the exclusion criteria will return to the clinic for randomization and treatment on Visit 2 (Day 1). At this visit, subjects will be randomized 2:2:1:1 to

receive pegcetacoplan monthly, pegcetacoplan every other month, sham injection monthly, or sham injection every other month, respectively. Randomization will be stratified according to GA lesion area at screening ($< 7.5 \text{ mm}^2$; $\ge 7.5 \text{ mm}^2$), and presence of CNV in the fellow eye.

All subjects will be assessed monthly during the first 12 months regardless of treatment regimen. From Month 12 to Month 24, subjects will follow the outlined visit schedule (Appendix A to Appendix D) based on treatment assignment (ie, subjects in the monthly groups will be assessed monthly while subjects in the every-other-month [EOM] groups will be assessed every other month). The last visit in the study will be at Month 24, approximately 30 days (monthly treatment group) or 60 days (EOM treatment group) after the last visit at which investigational product is administered. At the end of the 24-month study period, subjects will have the option to enroll into a separate open-label study.

Subjects who discontinue study treatment can continue participation in the study and should be encouraged to return to the clinical site for as many follow-up visits as they can (with the exception of pegcetacoplan/sham administration). Subjects who wish to fully withdraw from the study before Month 24, should be encouraged to complete the early termination visit.

Endpoints and statistical analysis:

Endpoints

Primary Efficacy Endpoint

• Change from baseline to Month 12 in total area of GA lesion(s) in the study eye (in mm²) based on fundus autofluorescence (FAF).

Key Secondary Efficacy Endpoints

- Change from baseline in monocular maximum reading speed (study eye), as assessed by MNREAD or Radner Reading Charts at Month 24 (in select countries)

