## **4. STATISTICAL ANALYSIS SETS**

Two sham treatment arms (SM and SEOM) will be pooled into a single control (Sham) group for analyses.

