#### **6.3.2.4. NL-BCVA Score**

The mean NL-BCVA score for the study eye will be summarized and analyzed in a similar fashion as the primary efficacy endpoint using MMRM described in Section 6.2.2. The model will include treatment (PM, PEOM, Sham), presence of CNV in the fellow eye (yes or no), and baseline GA lesion area ( $< 7.5 \text{ mm}^2$  or  $\geq 7.5 \text{ mm}^2$ ) as fixed effects; baseline NL-BCVA score as a covariate, time (in months) as a factor; the time  $\times$  treatment interaction term as well as the baseline NL-BCVA score  $\times$  time interaction term. Note, for the second year, only timepoints that were measured for all three treatment groups will be included in the model.

The observed values for the NL-BCVA will be summarized by treatment group and visit for both the study and the fellow eye. Summaries will present the descriptive statistics for baseline, absolute values and change from baseline data.

The mean change from baseline in the NL-BCVA score for the study eye  $\pm$  the standard error as well as the LS mean of the change from baseline in the NL-BCVA score for the study eye  $\pm$  the standard error will be plotted over time by treatment group.

In addition, the categorical changes (improvements of  $\geq 15$ ,  $\geq 10$  to  $< 15$ ,  $\geq 5$  to  $< 10$ , and minimal/no change ( $-4$  to  $4$ ), worsening of  $\geq 5$  to  $< 10$ , and  $\geq 10$  to  $< 15$  and  $\geq 15$ ) for the study eye will be summarized by treatment group and visit.

The shift from baseline in the NL-BCVA of the study eye categories ( $\geq 70$ ,  $\geq 60 - < 70$ ,  $\geq 35 - < 60$ ,  $\geq 20 - < 35$ ,  $< 20$  ETDRS letters over time will be presented by treatment group and visit.

The above-mentioned ETDRS letter thresholds are based on WHO definitions for vision impairment and blindness. WHO criteria were implemented in an attempt to capture the progressive nature of Geographic Atrophy and the ultimate treatment goal of avoiding successive vision impairment and blindness through application of active treatment (Pegcetacoplan vs. Sham).

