#### **6.4.1. Low Luminance Best-Corrected Visual Acuity (LL-BCVA)**

LL-BCVA of the study eye will be summarized and analyzed in the similar fashion as the primary efficacy endpoint using MMRM described in Section 6.2.2. The model will include treatment (PM, PEOM, Sham), presence of CNV in the fellow eye (yes or no), and baseline GA lesion area ( $< 7.5 \text{ mm}^2$  or  $\geq 7.5 \text{ mm}^2$ ) as fixed effects; baseline LL-BCVA score as a covariate, time (in months) as a factor; the time  $\times$  treatment interaction term as well as the baseline LL-BCVA score  $\times$  time interaction term. Note, for the second year, only timepoints that were measured for all three treatment groups will be included in the model.

The observed values for the LL-BCVA will be summarized by treatment group and visit for both the study and the fellow eye. Summaries will present the descriptive statistics for baseline, absolute values and change from baseline data.

The mean change from baseline in the LL-BCVA score in the study eye  $\pm$  the standard error as well as the LS mean of the change from baseline in the LL-BCVA score in the study eye  $\pm$  the standard error will be plotted over time by treatment group.

The categorical changes (improvements of  $\geq 15$ ,  $\geq 10$  to  $< 15$ ,  $\geq 5$  to  $< 10$ , and minimal/no change ( $-4$  to  $4$ ), worsening of  $\geq 5$  to  $< 10$ , and  $\geq 10$  to  $< 15$  and  $\geq 15$ ) for the study eye will be summarized by treatment group and visit.

Additionally, the average LL-BCVA score over the last 3 months for each reporting period (Month 10 - Month 12 for the Month 12 reporting; Month 22 - Month 24 for the Month 24 reporting) will be calculated for each subject who has at least one LL-BCVA assessment in these windows. The observed values for the LL-BCVA and changes from baseline will be summarized by treatment group for the study eye. Summaries will present the descriptive statistics for baseline, absolute values and change from baseline data.

The same subgroup analyses as described for NL-BCVA in Section 6.3.5 will also be repeated for LL-BCVA for the full 24 months.

All LL-BCVA data will be listed for the ITT set. In addition, the low luminance deficit will be calculated as the difference between NL-BCVA and LL-BCVA and listed for the ITT set.

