## **13. DATA HANDLING CONVENTIONS**

### **13.1. General Data Reporting Conventions**

Continuous variables will be summarized using the number of non-missing observations (n), mean, SD, median, quartile 1, quartile 3, minimum, and maximum. Categorical variables will be summarized using frequencies and percentages. Unless stated otherwise, for all percentages, the number of subjects in the analysis population for the treatment group will be the denominator.

Unless otherwise specified, the estimated mean and median for a set of values should be printed out to 1 more decimal place than the original values, and standard deviations should be printed out to 2 more decimal places than the original values. The minimum and maximum should report the same number of decimal places as the original values. Percentages will be displayed with 1 decimal place; except percentages will not be presented when the count is zero and 100% will be presented as an integer.

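### At the six odd months of Year 2, the letter-loss table in SAP 7.6 defaults to a whole-group denominator although the every-other-month arms have no scheduled reading, so pooled sham shows about half its rate and PEOM shows zero

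*SAP*

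**What the plan says.** SAP 7.6 asks for "The number and percentage of subjects who lost letters compared with baseline at each visit based on NL-BCVA" in each eye, in three loss categories (15 or more letters, 15 to under 30, and 30 or more). It restricts neither the visits nor the denominator. Four other provisions then determine what the table shows:

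- **Denominator.** SAP 13.1: "Unless stated otherwise, for all percentages, the number of subjects in the analysis population for the treatment group will be the denominator". For safety output that population is set in SAP 7: "Unless otherwise specified, all safety summaries will be performed on the Safety set".
- **Pooling.** SAP 4: "Two sham treatment arms (SM and SEOM) will be pooled into a single control (Sham) group for analyses".
- **Year 2 visits.** Protocol synopsis: "subjects in the monthly groups will be assessed monthly while subjects in the every-other-month [EOM] groups will be assessed every other month". In the BCVA rows of Protocol Appendices B and D (SAP Tables 10 and 12), the monthly arms are read at every month from 13 to 24. The every-other-month arms are read only at Months 14, 16, 18, 20, 22 and 24.
- **Windows.** SAP Table 6, which maps unscheduled and early-termination visits in the every-other-month regimen, has no odd-month window after Month 11. Such readings go to an even month.

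The SAP departs from these defaults in other places. Sections 7.2 and 7.3 base the laboratory and vital-sign percentages on subjects who have a value at the visit. Section 6.3.2.4 limits the NL-BCVA model: "for the second year, only timepoints that were measured for all three treatment groups will be included in the model". Section 6.4.1 does the same for LL-BCVA. Those two restrictions cover the models only. The categorical changes in the same sections are still tabulated by visit; in 6.4.1 they "for the study eye will be summarized by treatment group and visit".

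**The concern.** Letter loss on NL-BCVA is a listed safety endpoint (SAP 2.2.5). When a subject with no scheduled reading stays in the denominator, that subject is in effect counted as not having lost vision. At the odd months of Year 2 this applies to all of PEOM and half of pooled sham, but to nobody on PM beyond ordinary dropout.

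Readers will look closely at vision loss by regimen. Protocol 4.1.4 reports new active study-eye CNV in Phase 2 in 18 PM, 7 PEOM and 1 sham subject. In that setting an artificial excess on PM could be taken for a safety signal, and an artificial zero on PEOM could reassure falsely. SAP 11 also allows Month 12 to 24 data to be cut and summarised for regulatory submissions before final lock, so odd-month rows may be read before Month 24 is complete.

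**Working it through.** **Arm sizes.** About 600 subjects at 2:2:1:1 gives 600 × 2/6 = 200 (PM), 200 (PEOM), 600 × 1/6 = 100 (SM) and 100 (SEOM). This matches Protocol Table 1. Pooled sham is 100 + 100 = 200. The Safety set is taken to be about the same size.

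**Assumed input.** The documents give no true proportion *p* losing 15 or more letters. It is varied from 5% to 25% and held equal in all arms.

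**Formula.** Under SAP 13.1, the percentage shown at a visit = (number assessed × *p*) / (group size).

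**Odd months of Year 2, full retention.**

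- PM: 200*p*/200 = *p*
- Pooled sham, SM only assessed: 100*p*/200 = *p*/2
- PEOM: 0/200 = 0 (SAP 13.1 prints no percentage when the count is zero, so the cell would show a bare 0)

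| True *p* | PM | Pooled sham | PEOM | PM:sham |
|---|---|---|---|---|
| 5% | 5% | 2.5% | 0 | 2.0 |
| 10% | 10% | 5% | 0 | 2.0 |
| 15% | 15% | 7.5% | 0 | 2.0 |
| 20% | 20% | 10% | 0 | 2.0 |
| 25% | 25% | 12.5% | 0 | 2.0 |

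At *p* = 10% the counts are 20 of 200 on PM and 10 of 200 on sham.

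**Retention.** Let *r* be the fraction still assessed. The ratio is *r*(PM) / (0.5 × *r*(SM)). If the two fractions are equal it is 2.0. Over an assumed range of 80% to 100%, the extremes are 0.8 / (0.5 × 1.0) = 1.6 and 1.0 / (0.5 × 0.8) = 2.5.

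**Even months, including Month 24.** All arms are scheduled. At *p* = 10%: PM 20/200 = 10%; sham (100 + 100) × 0.10 / 200 = 10%; ratio 1.0.

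**With subjects assessed at the visit as denominator.** At odd months PM = 200*p*/200 = *p* and sham = 100*p*/100 = *p*, ratio 1.0. PEOM has n = 0 and no percentage. The Sham column then holds SM subjects only.

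**The case against.** The strongest reply is that 7.6 never asks for a whole-group denominator. The section is silent, 13.1 applies only unless something else is stated, and where the SAP spells out a per-visit safety percentage (7.2 and 7.3) it uses subjects with values. A sensible programmer might do the same here. It is fair to call this an omission that triggers an unsuitable default rather than a chosen analysis. But nothing in 7.6 displaces the default, and the explicit wording in 7.2 and 7.3 suggests that an exception has to be written down.

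A second reply is that the artefact would be conspicuous. PEOM would drop to zero in alternate months and sham would fall and recover. The observed-value NL-BCVA summaries report the number of non-missing readings, which would expose the gap. That lowers the risk of misreading but does not make the printed percentages correct.

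Third, the categorical-change tables in 6.3.2.4 and 6.4.1 are a weaker case, and this stands. They run from improvement to worsening, so at odd months pooled sham would total about 50% and PEOM 0%. The missing readings show within the table, and gains and losses are shrunk alike.

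Fourth, deleting the odd-month rows would remove scheduled PM and SM safety readings from the summary. This also stands: PM against SM is a valid same-regimen comparison, so deletion should be optional.

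**Conclusion.** The point holds for six rows of one descriptive safety table: Months 13, 15, 17, 19, 21 and 23 in SAP 7.6, with the SAP 13.1 default applied as written. Given equal true risk and equal PM and SM retention, pooled sham shows about half its rate, PEOM shows zero and PM shows its full rate. The PM:sham ratio is about 2.0 for any *p*, and roughly 1.6 to 2.5 if retention differs between 80% and 100%.

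A reader might infer that sham vision loss is halved throughout Year 2 or at the final timepoint. The schedules do not support that: Month 24, the other even months, and Year 1 under the standard schedule have readings planned in every arm. Nor is any formal conclusion at risk. No hypothesis test uses this table, and the NL-BCVA model is already confined to common Year 2 timepoints.

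A smaller version can arise in Year 1 under the COVID-19 minimum schedule, which drops BCVA for every-other-month subjects at non-dosing visits. Its size depends on how many subjects followed that schedule, which the documents do not say.

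The correction is worth making because following a stated rule gives wrong percentages for a listed safety endpoint, and it costs very little.

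**What to change.** 1. In SAP 7.6, state that the denominator at each visit is the number of subjects with a baseline and an NL-BCVA value at that visit, and display that n. This follows the values-at-visit approach of 7.2 and 7.3, and it also covers the Year 1 COVID-19 case.
2. For the odd months of Year 2, choose one of two presentations. Either limit the three-group table to visits scheduled in both regimens (Months 14, 16, 18, 20, 22 and 24), or keep the odd-month rows and label them monthly regimen only, PM vs SM. A label is needed even with the corrected denominator, because the Sham column then contains SM alone.
3. For consistency, apply the same wording to the NL-BCVA and LL-BCVA categorical-change tables in 6.3.2.4 and 6.4.1.

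The cost is one or two sentences of SAP text. Limiting the visits moves six scheduled PM and SM readings from the summary to listings. Labelling the rows keeps them in view, with about 100 sham subjects and an empty PEOM cell.
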